14.2.2 Serious AEs

A serious adverse event (SAE) is any event that meets one or more of the following criteria:

- Leads to a death
- Leads to a serious deterioration in the health of a subject that:
 - Resulted in a life-threatening illness or injury
 - Resulted in a permanent impairment of a body structure or a body function
 - Required in-patient hospitalization or prolongation of existing hospitalization*
 - Resulted in medical or surgical intervention to prevent permanent impairment to body structure or a body function
- Leads to fetal distress, fetal death or a congenital abnormality or birth defect.

“Hospitalization” means the event necessitated an admission to a health care facility e.g., with at least an overnight stay. Emergency room visits that do not result in admission to the hospital should be evaluated for one of the other serious outcomes.

*Planned hospitalization for a condition present prior to the participant’s enrollment in the study will **not meet** the definition of an SAE but should nevertheless be included in routine study reporting.

14.2.3 Non-Serious AEs

A non-serious AE is any event that results in minimal transient impairment of a body function or damage to a body structure and does not require any intervention listed under the criteria for “Serious Adverse Event.” Non-serious adverse events require routine reporting via EDC.

14.2.4 Anticipated AEs

An anticipated AE is one that has been reported in previous studies of cardiac ablation and can be anticipated in this current study as per the risk analysis. Appendix IV provides a comprehensive list of anticipated AEs. If listed then report event as anticipated.

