11.2 Sponsor Responsibilities

The Sponsor (Biosense Webster) will be responsible for the following:

- Preparing study documents including but not limited to the protocol, eCRFs and template informed consent
- Completing pre-study site assessments and approvals
- Obtaining approval from FDA and regulatory agencies, as applicable
- Obtain signed study contracts from investigators/hospitals, contract research organizations, or other involved parties.
- Providing protocol and device training to investigators and research personnel, as applicable
- Instructing operators and technicians in the proper use and monitoring of study devices
- Monitoring the study throughout the duration of the investigation
- Securing investigator/site compliance with the protocol and applicable regulations
- Creation and maintenance of eCRF database
- Conducting all communications with regulatory agencies

- Submitting study supplements for regulatory approval (e.g., request for study expansion), as necessary
- Preparing reports summarizing the status of the clinical study no less often than annually, which will be supplied to FDA and to other regulatory agencies, as applicable. Annual reports may also be provided to the Principal Investigator
- Preparing and submitting the final clinical study report to FDA and applicable regulatory agencies
- Having AEs reviewed by the study specific committees and/or study specific reviewers, as required
- Report the results of an evaluation of an unanticipated adverse device effect to FDA within 10 working days after receiving notice of the adverse effect.
- Register the study with ClinicalTrials.com no later than 21 calendar days after enrolling the first subject and submit study results on all pre-specified outcomes, including negative outcomes to ClinicalTrials.gov no later than one year after completion of the primary endpoint (unless an extension has been approved via certification from the Secretary of Health and Human Services). Results submission could be delayed if an extension is granted to the results submission deadline; however, the release of all results on pre-specified outcomes will be hastened if the study is terminated early.

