14.2.5 Unanticipated Serious Adverse Device Effects

A (serious) adverse device effect (SADE) is any (serious) adverse effect on subjects’ health, safety, rights, welfare, and life-threatening problems including death, which is caused by, or associated with the study device. Accordingly, relationship to device or study is a crucial assessment by investigators. An

unanticipated adverse device effect (UADE) or unanticipated serious adverse device effect (USADE) is any ADE or SADE that has not been previously identified in nature, severity, or degree of incidence in the study plan or risk analysis report. An investigator shall submit to the reviewing IRB a report of any unanticipated adverse device effect occurring during an investigation per IRB requirements.

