20.2.1 Records

Records to be maintained by the investigator include:

- Study protocol and all amendments with signature pages
- Signed clinical study agreement and Statement of Investigator
- IRB approval letters, including approved ICF documents
- Evidence of IRB compliance
- Other significant IRB correspondence

- Significant sponsor correspondence relating to the study
- CVs for all investigator(s)
- Financial Disclosure for key study staff
- Records of protocol and supporting training
- Site personnel delegation of authority/responsibility log
- Clinical Monitor/Site Visit sign-in log
- Device accountability log
- Reports (e.g., annual reports, final reports from investigator and Sponsor).

The following records must be maintained for each subject enrolled in the study:

- Signed Patient ICF
- All completed electronic CRFs and supporting source documentation
- Supporting documentation of any AEs and/or death.

The investigator must retain copies of procedure reports, procedure nursing notes and the results of any interventional procedures that occur while the subject is enrolled in the study. The Sponsor reserves the right to secure data clarification and additional medical documentation on subjects enrolled in this study.

21. Clinical Compliance and Quality Control

Quality Control (QC) procedures will be implemented beginning with the data entry system, and ongoing QC checks will be run on the database. Any missing data or data anomalies will be communicated to the site(s) for clarification/resolution.

Following written Standard Operating Procedures (SOPs), monitors will verify that the clinical trial is conducted and data are generated, documented, and reported in compliance with the protocol, GCP, and the applicable regulatory requirements. If noncompliance is identified, Sponsor is required by regulation to implement measures to secure compliance.

The investigational site will provide direct access to all trial related sites, source data/documents, and reports for the purpose of monitoring and auditing by the sponsor, and inspection by local and regulatory authorities.

22. Study Suspension or Termination

The study may be suspended or terminated early at the discretion of the Sponsor, for reasons such as incidence of unanticipated serious adverse device effects that may pose a risk to other subjects. In any early termination, already enrolled subjects will continue to be followed per the study protocol requirements.

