25.3 APPENDIX III. Study Definitions

Term	Definition
Adverse Event (AE)	
Any unfavorable and unintended sign, medical occurrence, disease or injury (including abnormal laboratory findings) in subjects, users or other persons temporally associated with the use of a medicinal product or device whether or not related to the sponsor's product.
 
This definition includes events related to the medical device and/or the comparator, and events related to the procedure in which the device was used.

Adverse Device Effects (ADE's)	Adverse events related to the use of the medical device. This definition includes adverse events resulting from insufficient or inadequate instructions for use deployment, implantation, installation, or operation, or any malfunction of the medical device. This definition includes any event resulting from use errors or from intentional misuse of the investigation medical device.
AF/AT/AFL of unknown origin Episode	An episode of AF/AT/AFL of unknown origin ⁺ ≥ 30 seconds in duration.
AF Episode	An atrial fibrillation episode is defined as AF which is documented by ECG monitoring and has a duration of at least 30 seconds, or if less than 30 seconds, is present continuously throughout the ECG monitoring tracing. The presence of subsequent episodes of AF requires that sinus rhythm be documented by ECG monitoring between AF episodes
Anticipated AE	An effect which by its nature, incidence, severity or outcome has been identified as possible complications associated with the medical device and/ or intervention procedure.
Atypical Flutter	Macro-reentrant circuits within the atria where activation rotates around large obstacles that does not meet the criteria for Typical Flutter.

Term	Definition

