Unanticipated Serious Adverse Device Effect (USADE)	Serious adverse device effect which by its nature, incidence, severity or outcome has not been identified in the current version of the risk analysis report. NOTE: Anticipated SADE: an effect which by its nature, incidence, severity or outcome has been previously identified in the risk analysis report
Ventricular Tachycardia (VT)	Ventricular tachycardia: a tachycardia (rate $\geq 100/\text{min}$) with three or more consecutive beats that originates from the ventricles independent of atrial or AV nodal conduction. Continuous VT for $\geq 30\text{ s}$ or that requires an intervention for termination (such as cardioversion).

[†]AFL of unknown origin is defined as all AFL except those CTI dependent AFL as confirmed by 12-Lead ECG and entrainment maneuvers in an EP study.

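### Section 14.2.4 makes any event on the Appendix IV list anticipated by name alone, in conflict with the severity and incidence tests for a UADE/USADE in 14.2.5 and Appendix III

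*Protocol*

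**What the plan says.** Protocol 14.2.4 opens by describing an anticipated AE as one seen in earlier cardiac ablation studies and expected here on the basis of the risk analysis. It continues: "Appendix IV provides a comprehensive list of anticipated AEs". It closes with an instruction that carries no condition: "If listed then report event as anticipated".

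Three other passages use a wider test:

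- Protocol 14.2.5 defines a UADE or USADE as "any ADE or SADE that has not been previously identified in nature, severity, or degree of incidence in the study plan or risk analysis report".
- Appendix III defines an Anticipated AE as "An effect which by its nature, incidence, severity or outcome has been identified as possible complications associated with the medical device" and/or the intervention procedure.
- Appendix III defines a USADE as "Serious adverse device effect which by its nature, incidence, severity or outcome has not been identified in the current version of the risk analysis report".

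Four things depend on UADE or USADE status:

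- The investigator reports UADEs to the IRB (14.2.5).
- The sponsor must "Report the results of an evaluation of an unanticipated adverse device effect to FDA within 10 working days" of receiving notice (11.2).
- UADE incidence is an additional safety endpoint (protocol 9.2.4.1, SAP 8.4.3.1).
- Section 22 gives, as an example of a reason to suspend or terminate, the "incidence of unanticipated serious adverse device effects that may pose a risk to other subjects".

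**The concern.** A site following 14.2.4 checks one thing: whether the term is in Appendix IV. A site following 14.2.5 must also ask whether the severity or frequency goes beyond what was identified. For a listed event these two instructions can give opposite answers, and nothing in the protocol says which prevails.

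Appendix IV is broad enough for this to matter in practice. Besides specific complications it lists Death, Cardiac arrest, Heart injury, Hemorrhage, Inflammation and Toxic reaction. If nearly every plausible device effect is on the list, the site check will almost always return the same answer. The label then carries little information about severity or frequency, which are the features that the UADE definition is meant to pick up.

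**Working it through.** The plan states no figure to reproduce, so the check sets the passages side by side.

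**Step 1. The tests compared.**

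| Place | Severity? | Incidence? | Outcome? |
|---|---|---|---|
| 14.2.4, last sentence | no | no | no |
| 14.2.5, UADE/USADE | yes | yes | no |
| Appendix III, Anticipated AE | yes | yes | yes |
| Appendix III, USADE | yes | yes | yes |

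The sentence in 14.2.4 is the only one of the four that stops at the name of the event.

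**Step 2. Can the wording be reconciled?** One could read 14.2.5 as requiring that nature, severity and incidence all be unidentified. But an event whose nature has not been identified has no identified severity or rate either, so severity and incidence would then add nothing. They have work to do only if an event of known nature can still be unanticipated, and that is the case that 14.2.4 closes off.

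**Step 3. How much does the list cover?** The primary safety endpoint has 14 categories. Each has an entry or an equivalent in Appendix IV: for example, phrenic nerve damage and diaphragmatic paralysis for phrenic nerve paralysis, periesophageal vagal nerve injury and gastroparesis for vagal injury, and vascular bleeding, AV fistula and pseudoaneurysm for vascular complications. The list gives no rates. Severity appears only in a few entries, such as effusion with or without tamponade and complete or incomplete heart block.

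**Step 4. Is there anything to test incidence against?** Yes. Protocol 6.4.2 quotes death in AF ablation at <0.1% to 0.4%, thromboembolism at 1% to 2%, and perforation at <1% with RF catheters. It also says that atrio-esophageal fistula, PV stenosis and vagal nerve injury have not been reported after pulsed field ablation. All of these events are in Appendix IV, so under 14.2.4 even a cluster of them would be reported as anticipated.

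**Step 5. Who could see an incidence signal?** As an illustration, take the maximum pivotal enrollment of 408 over 40 sites and the upper thromboembolism figure of 2%:

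- Average site: 408 / 40 = 10.2 subjects; 10.2 × 0.02 = 0.20 expected events.
- Largest site under the 15% cap: 0.15 × 408 = 61.2 subjects; 61.2 × 0.02 = 1.2 expected events.

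Fewer sites would raise the average. Either way a single site cannot judge incidence, so that part of the test needs pooled data and belongs with the sponsor.

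**Step 6. Does another passage repair the rule?** Section 14.1 tells investigators to judge seriousness and relationship, not anticipated status. Section 14.4 gives the sponsor review of classification, which could include anticipated status but does not name it. Section 14.9 provides aggregate review for trends, and 14.10 a DMC. None requires a listed event to be re-tested on severity or incidence.

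**The case against.** The strongest reply is that this is one loose sentence set against three consistent passages. The first sentence of 14.2.4 already points to the risk analysis, and 14.2.5, the specific rule for device effects, makes no exception for listed terms.

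The sponsor-level consequences are also not tied to the site's list check. The FDA report concerns the results of an evaluation and is a sponsor duty. Section 22 leaves suspension to the sponsor's discretion and introduces its reason with *such as*. The visible text does not say that the UADE endpoint is counted from site labels, and SAP 8.13 makes that endpoint descriptive. SAEs and SADEs reach the sponsor within the same 72 hours as UADEs. Deaths and primary adverse events are reported immediately (14.2). For SADEs, anticipated or not, the sponsor must decide whether the risk analysis needs updating (14.4).

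Most of this stands, and it limits the harm. It does not remove the conflict, because 14.2.4 is the operative instruction to the site and the IRB report is the investigator's own duty. One timing effect also remains: a non-serious device effect labelled anticipated could take the two-week routine route instead of the 72-hour UADE route.

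A reader might go further and infer that listed events escape UADE handling altogether, that the UADE count is driven to zero, or that the study's only stopping ground is disabled. The documents support none of these, for the reasons above. Nor would a single device-related death be unanticipated by severity, since a listed death cannot be exceeded in severity; incidence is the relevant test there. A run of strokes within seven days of ablation would still count against the 12% safety performance goal and go to the CEC, whatever its label.

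**Conclusion.** The contradiction is real and should be fixed. At site level the rule misclassifies a listed device effect of unexpected severity or incidence and leaves the investigator without a trigger for the IRB report. At sponsor level such an event can be missed for the FDA evaluation report, the UADE endpoint and the Section 22 example, but it need not be. Reporting of serious events to the sponsor within 72 hours is unaffected, and so are the primary endpoints, hypotheses, sample size and analysis sets. For that reason it does not rank among the changes on which the trial's conclusions depend.

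The Safety Management Plan, DMC charter and risk analysis report are not among the documents. If the Safety Management Plan already assigns the UADE determination to the sponsor, the remaining problem is the site instruction and the link to the IRB report.

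**What to change.** Replace the last sentence of 14.2.4 with a statement that:

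1. listing in Appendix IV makes an event anticipated by nature only;
2. a device-related event whose severity, outcome or incidence exceeds what the study plan or risk analysis report identifies is a UADE/USADE under 14.2.5, even if it is listed;
3. the sponsor makes and documents this determination for every ADE and SADE, and informs the site so that the IRB report can follow.

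State in the SAP that the incidence of UADEs (8.4.3.1, 8.13.1) is counted from the sponsor's determination, and align the Safety Management Plan with it.

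The cost is a short text change and a few more sponsor assessments, since the sponsor already reviews AE classification under 14.4. The UADE count may come out slightly higher.

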14.2.5 Unanticipated Serious Adverse Device Effects

A (serious) adverse device effect (SADE) is any (serious) adverse effect on subjects’ health, safety, rights, welfare, and life-threatening problems including death, which is caused by, or associated with the study device. Accordingly, relationship to device or study is a crucial assessment by investigators. An

unanticipated adverse device effect (UADE) or unanticipated serious adverse device effect (USADE) is any ADE or SADE that has not been previously identified in nature, severity, or degree of incidence in the study plan or risk analysis report. An investigator shall submit to the reviewing IRB a report of any unanticipated adverse device effect occurring during an investigation per IRB requirements.

14.3 Clinical Investigation Device Failure/Malfunction/Deficiency

A device has failed if it does not perform according to the instructions for use or fails to meet the expectations of the device and/or investigator (i.e., related to appearance of the device, performance, durability, safety, effectiveness, quality, reliability, labeling, etc.). If a device failure is detected or suspected, it should be documented on the appropriate CRF and the device must be promptly returned according to the Sponsor's instructions. If the device failure is associated with an AE, both the device failure and AE must be reported to the Sponsor immediately upon awareness (refer to Section 14.2).

14.4 Reporting Requirements

All serious AEs, UADE/SADE/USADE, and Study device failure/malfunction/deficiency, whether or not they are related to the device or procedure, must be reported by eCRF to the Sponsor (Biosense Webster Clinical Operations).

The Sponsor is responsible for reviewing AEs (e.g., causality, classification, seriousness) and for ongoing safety evaluations in accordance with the study safety management plan. In case of disagreement between the Sponsor and the principal investigator(s) that remain after query resolution, the Sponsor shall communicate both opinions to the concerned parties.

The Sponsor will ensure that investigators are instructed to return devices suspected of causing an AE or SAE (i.e., definitely device-related, probably device-related, or possibly device-related) in accordance with relevant regulations and current company procedures.

In the case of serious adverse device effects and device deficiencies that could have led to serious adverse device effects, the Sponsor will determine whether the risk analysis needs to be updated and whether corrective or preventive action is required.

Timing for reporting the different types of AEs is described in Table 14.4.1.

Table 14.4.1: Adverse Event Reporting Requirements

Type of Adverse Event	Reporting Requirements
Serious Adverse Events	Report to Sponsor as soon as possible but no later than 72 hours upon awareness of the event
UADE, USADE & SADE	Report to Sponsor as soon as possible but no later than 72 hours upon awareness of the event
Study device deficiency associated with an AE	Report both study device deficiency and AE to Sponsor as soon as possible but no later than 72 hours upon awareness of the event

All other Adverse Events	Routine reporting via eCRF as soon as possible but no later than 2 weeks upon awareness of the event
--------------------------	--

14.5 Intensity or Severity

Intensity (or severity) of AEs is defined as follows:

Table 14.2.5.1: Intensity or Severity Definitions

Mild	Events that result in minimal transient impairment of a body function or damage to a body structure, and/or does not require intervention other than monitoring.
Moderate	Events that result in moderate transient impairment of a body function or damage to a body structure, or that require intervention, such as the administration of medication, to prevent permanent impairment of a body function or damage to a body structure.
Severe	Events that are life threatening and/or result in permanent impairment of body functions or damage to body structures, or that require significant intervention, such as major surgery, to prevent permanent impairment of a body function or damage to a body structure.

Intermittent AEs should be classified according to their greatest severity.

14.6 Outcome

AE outcomes are assessed according to the following classifications:

Table 14.6.1: Adverse Event Outcome Classifications

Recovered/ Resolved without Sequelae	Subject fully recovered with no observable residual effects.
Recovering/ Resolving	Subject's condition is improving but residual effects remain.
Recovered/ Resolved with Sequelae	Subject recovered with observable residual effects.
Not recovered/ resolved	AE is ongoing without improvement in overall condition
Fatal	Subject died as a result of the adverse event, whether or not the AE is related to the device or procedure. Note: deaths from any cause occurring on this study are to follow expedited reporting.
Unknown	AE outcome is unknown (e.g., subject lost to follow-up)

14.7 Causality

Causality of AEs is defined as follows:

Table 14.7.1: Adverse Event Causality Classifications

Caused By	Relation	Definition of Relation
Device	Definitely (Causal Relationship)	The event is associated with the investigational device beyond reasonable doubt
	Probable	The relationship with the use of the investigational device seems relevant and/or the event cannot reasonably be explained by another cause, but additional information may be obtained
	Possible	The relationship with the use of the investigational device is weak but cannot be ruled out completely
	Not related	Relationship to the investigational device can be excluded
Study Procedure	Definitely (Causal Relationship)	The event is associated with the procedure beyond reasonable doubt. ¹
	Probable	The relationship with the study procedure seems relevant and/or the event cannot be reasonably explained by another cause, but additional information may be obtained
	Possible	The relationship with the study procedure is weak but cannot be ruled out completely
	Not related	Relationship to the procedure can be excluded

¹If event is deemed related to procedure, site should indicate whether related to index or repeat if applicable.

